One hundred smokers will be recruited from the New Haven area through newspaper, and radio advertisements and fliers. The study will be described over the telephone. Subjects will be given a brief tobacco use history and medical screening questionnaire. Eligible subjects will be invited to a single screening evaluation. The screening evaluation will include the following: a) obtaining an informed consent; b) tobacco use history via the Fagerstrom Test of Nicotine Dependence (FTND) and DSM-5 Tobacco Use Disorder (TUD) criteria; d) urine cotinine levels determined with a NicAlert test strip (info: www.nymox.com/default.action?itemid=47). If subjects are eligible they will be invited to participate in a second evaluation, which will include: a) complete physical and psychiatric examination including the structured clinical interview (SCID) for DSM-5 criteria; b) a complete physical and laboratory examination including CBC, TSH, ALT, AST, GGT, alkaline phosphatase, glucose, BUN and creatinine; c) urine analysis for drug screening, and for women, urine pregnancy test; and d) ECG

Inclusion criteria: 1) Female and male smokers, aged 18 to 35 years, who have been smoking tobacco cigarettes for at least a year; 2) smoke ≥ 5 and less than 20 cigarettes per day; 3) urine cotinine levels > 100 ng/mL consistent with nicotine intake of an active smoker (23); 4) not seeking treatment at the time of the study for nicotine dependence; 5) in good health as verified by medical history, screening examination, and screening laboratory tests; and 6) for women, not pregnant as determined by pregnancy screening, nor breast feeding, and using acceptable birth control methods.

Exclusion criteria: 1) history of major medical or psychiatric disorders that the physician investigator deems as contraindicated for the subject to be in the study; 2) regular use of psychotropic medication (antidepressants, antipsychotics, or anxiolytics); 3) current alcohol or substance dependence for any other recreational or prescription drugs other than nicotine; 5) use of e-cigarettes more than 10 days in the past 30 days; 6) urine drug screening indicating recent illicit drugs use (with the exception of marijuana).

Justification for age criteria: The study will enroll young adults between the ages of 18 to 35 to minimize variation in the number of years of smoking that can influence measures of dependence including withdrawal severity (24, 25).

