Justification to include smokeless tobacco and e-cigarette users: We will include users of smokeless tobacco or e-cigarettes given the high prevalence of e-cigarette and smokeless tobacco products among young adults (26-28). As noted above, urine cotinine will be used to biochemically confirm the subjects' nicotine consumption and smoking status and used as a covariate in all analyses if required.

Subject sampling to account for sex, race, dependence symptoms, and smoking frequency: We are planning to enroll Caucasian and African-American smokers while maintaining an approximately equal male-to-female ratio.

We will create dichotomous variables to be used as a covariate to match groups on race (European American and African American) and sex because of the potential influence of race and sex on smoking behavior and nicotine pharmacokinetics (22, 29). We will also control for differences in the frequency of smoking because it may influence the behavioral effects nicotine (30-32); a continuous variable based on the reported smoking frequency (cigs per day) will be used as a covariate in the analyses if required.

8: Recruitment:

Hundred subjects will be recruited. The goal is to have 70 completers, 35 menthol and 35 non-menthol cigarette smokers.

9. Research Plan:

A. Overview

Experimental Summary: Subjects will complete five separate experimental sessions on five separate days with each session beginning around 8 AM (Fig 2). Each session (1 to 15 days apart) will include one infusion condition that will be either saline or nicotine at four different infusion rates. The five infusion conditions will be assigned randomly to one of the five experimental sessions. All infusions will last 10 minutes and be controlled by two infusion pumps, a saline infusion pump and a nicotine infusion pump. The 0.24 mcg/kg/s condition will include a 1 minute infusion of nicotine followed by a 9 min infusion of saline; the 0.096 mcg/kg/s condition will include a 2.5 minute infusion followed by a 7.5 min infusion of saline; the 0.048 mcg/kg/s condition will include a 5 min infusion of nicotine followed by a 5 min infusion of saline; the 0.024 mcg/kg/s condition will include a 10 min infusion of nicotine and no infusion of saline; and the placebo condition will include a 10 min infusion of saline and no

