infusion of nicotine. The most rapid nicotine infusion rate, 0.24 mcg/kg/s, has proven to be well tolerated in our prior studies (12, 18-20, 22). The total weight-adjusted nicotine dose will not exceed 1.2 mg. Subjects will complete baseline assessments after an indwelling catheter is inserted into an antecubital vein for safety and drug administration. Immediately prior to the start of the infusion (@ min 0) and at intervals following the start of the infusion, heart rate, blood pressure, DEQ and withdrawal assessments will be taken as shown in **Fig 2**. At the end of the session (min 120), subjects will complete the Drug versus Money Multiple-Choice Form (\$MCP) (23).

Session procedures: Before the experimental session, subjects will be required to abstain from smoking for 10h, which will be verified by expired air CO levels \leq 10 ppm (33, 34). Subjects will also be asked to refrain from consuming alcoholic beverages and drugs prior study participation, which will be verified by urine drug screening and breathalyzer before the sessions. Subjects that are non-compliant will be rescheduled or, if they are repeatedly non-compliant, discharged from the study. Subjects will be instructed to drink their typical amount of caffeinated beverages to minimize caffeine withdrawal, which could confound the study measures. Subjects will be instructed not to eat for 4 h before the sessions to minimize heartburn or nausea that can be associated with IV nicotine administration. A light meal will be provided at the end of each session.

Fig # 2 Schedule of Events: Experimental Session*

| Time point | Measures and Events |
|------------|--|
| Baseline | CO, urine and blood samples, HR/BP, M-NWSC, BQSU, SAFTEE, CPT |
| 0 min | IV Infusion starts |
| 1 min | HR/BP, DEQ, plasma nicotine |
| 3 min | HR/BP, DEQ, plasma nicotine |
| 5 min | HR/BP, DEQ, plasma nicotine |
| 8 min | HR/BP, DEQ, plasma nicotine |
| 10 min | IV Infusion ends, plasma nicotine |
| 11 min | HR/BP, DEQ, BQSU, plasma nicotine |
| 12 min | HR/BP, plasma nicotine |
| 13 min | HR/BP, DEQ, plasma nicotine |
| 15 | HR/BP, DEQ, plasma nicotine |
| 18 | HR/BP, DEQ, plasma nicotine |
| 20 | HR/BP, DEQ, plasma nicotine |
| 25 | HR/BP, DEQ, |
| 30 min | HR/BP, DEQ, BQSU, CPT, M-NWSC |
| 40 | HR/BP, DEQ, plasma nicotine |
| 50 | HR/BP, DEQ, plasma nicotine |
| 60 | HR/BP, DEQ, BQSU, M-NWSC CPT, plasma nicotine |
| 90 | HR/BP, DEQ, BQSU, M-NWSC CPT, plasma nicotine |

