| 120 min | End of session, HR/BP, DEQ, plasma nicotine, M-NWSC, BQSU, SAFTEE, CPT |
| 180 min | Discharge |

*Saline infusions will follow each nicotine infusion to maintain a 10 min total infusion time for each experimental session. Abbreviations: CO: Alveolar carbon monoxide; HR/BP: Heart rate/Blood pressure; M-NWSC: Minnesota Nicotine Withdrawal Symptom Checklist; BQSU:

Brief Questionnaire of Smoking Urges; CPT: Continuous Performance Test; DEQ: Drug Effects Questionnaire; SAFTEE: Systematic Assessment for Treatment Emergent Events.

B. Medical Monitoring And Safety

Subjects will be given a thorough physical examination as part of the post-consent screening procedures. For nicotine administration sessions, a physician or a nurse will be present and subjects will be attached to a cardiac monitor as well as a blood pressure and heart rate monitoring device. One IV catheter will be in place in each arm or only one if two IV's can't be placed. Subjects will be administered nicotine only if the systolic blood pressure is < 150 mmHg and heart rate is < 90 beats/minute. The procedures will terminate if blood pressure at any time is >170/110 mm Hg, the heart rate is >130 beats/min, or if they develop signs and symptoms of nicotine toxicity. Subjects will remain in the laboratory for at least an hour after the experimental infusion administration. These procedures have been developed as part of our IND application for IV nicotine.

C. Measures

C.1 Intake Measures

- 1) Fagerstrom Test of Nicotine Dependence (FTND):** This self-report measure assesses the degree of nicotine dependence and has been used widely in smoking studies (Heatherton et al., 1991)
- 2) Center for Epidemiologic Studies Depression (CES-D) scale:** The CES-D is a 20-item self-report measure of depressive symptoms (35). This scale will be used at intake to control for baseline differences in depressive symptoms.
- 3) The Holmes-Rahe Life Stress Inventory (HRLSI):** This is a self-report measure of 43 common life events related with some degree of stress on an individual's life. The scale was developed by the psychologists T.J. Holmes and R. Rahe, who reported that serious physical disorders, such as myocardial infarction, peptic ulcer, infections, and a variety of psychiatric disorders were positively associated with the number of life stressors scale within a period of 1 year. This scale will be used at intake to control for baseline differences in life stress.

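### Minor safety gap: the protocol names a pregnancy test only at screening, and none of its written session checks would stop an infusion in an unrecognised pregnancy

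*Combined protocol and SAP*

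**What the plan says.** Section 7 places the pregnancy test in the second screening evaluation: "urine analysis for drug screening, and for women, urine pregnancy test". Inclusion criterion 6 relies on it: "for women, not pregnant as determined by pregnancy screening, nor breast feeding, and using acceptable birth control methods". Section 12 likewise bases eligibility on history, examination and laboratory work completed before the research begins.

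On timing, section 9.A says: "Each session (1 to 15 days apart) will include one infusion condition". There are five sessions, and no maximum is given for the time from screening to the first.

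Before each session, 9.A requires 10 h of smoking abstinence, verified by expired carbon monoxide, and abstinence from alcohol and drugs, "which will be verified by urine drug screening and breathalyzer before the sessions". The Fig 2 baseline row reads "CO, urine and blood samples, HR/BP, M-NWSC, BQSU, SAFTEE, CPT", with no list of what the urine is tested for. Section 9.C.2 also names a urine cotinine strip at baseline.

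The dosing rule in 9.B is: "Subjects will be administered nicotine only if the systolic blood pressure is < 150 mmHg and heart rate is < 90 beats/minute". Section 12 repeats it. Neither mentions pregnancy. Section 12.3 lets the investigator end participation when a participant's health or well-being may be threatened.

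**The concern.** The plan admits only women who are not pregnant, but by the last infusion the evidence for that can be 60 days old plus an unstated screening gap. The drug screen listed in the same screening item is repeated before sessions; the pregnancy test is not named again. A pregnancy that began after screening, or too shortly before it for the strip to show, would pass every written check. The discretionary stopping clause helps once a pregnancy is known, but it does not find one.

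What is at stake is participant safety, in a sample of adults aged 18 to 35 planned to be about half women. No estimate, test or power figure depends on it.

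**Working it through.** The plan gives no figure of its own to reproduce. The check is a count of intervals followed by an expected-number calculation.

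**Inputs from the documents**
- Sessions: 5, so 4 intervals of 1 to 15 days (9.A).
- Women: 70 completers (section 8), with the plan "maintaining an approximately equal male-to-female ratio" (section 7), so about 35.
- Active conditions: 4 of 5, in random order (9.A).

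**Assumptions not in the documents**
- Yearly pregnancy rate on birth control: 1% to 10%.
- The delay from conception to a positive strip is the same at every test (14 days, for illustration).

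**Span from first to last session**
- Shortest: 4 × 1 = 4 days. Longest: 4 × 15 = 60 days.

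**Pregnancies newly detected at sessions 2 to 5**

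With a 14-day delay, a strip at session 1 (day 0) finds conceptions up to day −14, and a strip on day 60 finds those up to day 46. The added window is 46 − (−14) = 60 days, the full span. The delay cancels. Subtracting it from the span would leave out conceptions in the two weeks before session 1, which later strips would find.

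Expected number = women × span/365 × yearly rate:
- 60-day span: 35 × 60/365 = 5.75 woman-years; × 0.01 to 0.10 = 0.06 to 0.58.
- Weekly sessions (28 days): 35 × 28/365 = 2.68 woman-years; 0.03 to 0.27.
- Consecutive days (4 days): 35 × 4/365 = 0.38 woman-years; 0.004 to 0.04.

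**Active infusions prevented at the 60-day span** (sessions on days 0, 15, 30, 45 and 60)

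Each 15-day block of conceptions first becomes detectable at session 2, 3, 4 or 5, and stops 4, 3, 2 or 1 sessions respectively.
- Session-days: 15 × (4 + 3 + 2 + 1) = 150.
- Per detected pregnancy: 150/60 = 2.5 sessions; × 4/5 active = 2.0 infusions.
- Whole study: 35 × 150 × 0.8/365 = 11.5; × 0.01 to 0.10 = 0.12 to 1.15 infusions.

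**Gap from screening to session 1** (length not stated)
- Each 30 days: 35 × 30/365 = 2.88 woman-years, or 0.03 to 0.29 pregnancies that a session-1 strip would find.
- Each of these would spare all four active infusions: 2.88 × 4 = 11.5; × 0.01 to 0.10 = 0.12 to 1.15 infusions per 30 days of gap.

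These counts include pregnancies that a woman might recognise and report herself, so under these assumptions they are upper figures for the unrecognised ones.

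**The case against.** The strongest objection is that the absence of a test cannot be shown. A reader might infer that no pregnancy testing happens at sessions, or that the study will knowingly infuse pregnant women. The documents support neither. Fig 2 collects urine at every session baseline and leaves the tests open. The consent pages are not in the supplied text. Sections 9.B and 12 tie the safety procedures to an IND that is not in hand. This stands: the point is only that the protocol body neither names a repeat test nor makes dosing depend on one.

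A reader might also infer a material added fetal exposure. That is not supported either. Birth control is required. Participants smoke at least 5 cigarettes a day, so at least 5 × 60 = 300 over the longest span. Section 9.D puts each active infusion at about one cigarette's nicotine. Four infusions are then at most 4/300 = 1.3% of cigarettes smoked over that span (a larger share over a shorter one). On session days "subjects will be required to abstain from smoking for 10h", so total intake may not rise at all. This also stands, and it keeps the point minor.

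Finally, the sizes rest on outside rates, and the largest needs every interval at its maximum. At an assumed false-positive rate of 0.1% to 1% per strip, 175 strips give 0.2 to 1.8 false positives, which could exceed the true ones. That is a reason for a confirmation step. It does not argue against testing, since the plan itself excludes pregnant women and the urine is already collected.

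**Conclusion.** The point holds as a minor safety gap. The protocol body names one pregnancy test, at screening, and its written session checks and dosing conditions would not stop an infusion in an unrecognised pregnancy that began after screening or shortly before it.

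At the 60-day span, retesting at sessions 2 to 5 would newly detect 0.06 to 0.58 pregnancies and prevent about 0.12 to 1.15 active infusions in the whole study. The detected pregnancies fall to 0.004 to 0.04 if sessions run on consecutive days. Any screening-to-session-1 gap adds about 0.03 to 0.29 pregnancies per 30 days. All of this assumes 35 women, a yearly rate of 1% to 10% and the same strip delay at each test.

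The case for a change rests on upholding the plan's own exclusion at trivial cost, not on a large expected harm.

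**What to change.** For women, run a urine pregnancy test on the urine already collected at each session baseline, and name it in the Fig 2 baseline row. Add a negative pregnancy test that day to the dosing conditions in sections 9.B and 12. Apply it at all five sessions, saline included, so that the check does not depend on the assigned condition.

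State what follows a positive result: that day's infusion is withheld and the result is confirmed by a repeat test. A confirmed positive ends further infusions; an unconfirmed one leads to a rescheduled session. If the session urine panel, the IND procedures or the consent form already require the test, one sentence in the protocol saying so is enough.

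Cost: 35 × 5 = 175 strips, or at most 50 × 5 = 250 if half of the 100 recruits were women and all attended every session. No routine extra visit or sample is needed. A few false positives are possible (0.25 to 2.5 in 250 strips at the rates assumed above), each costing a confirmatory test and perhaps a rescheduled session. Very recent conceptions would still be missed. Design, power and analysis do not change.

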The peak nicotine concentration in blood, ~8 ng/ml, was approximately 12 minutes after the initiation of 15 puffs, with one puff every 30s (5). ECs deliver nicotine slower than tobacco cigarettes, probably because EC vapor does not penetrate as deeply into the lung tissue as cigarette smoke for most users. High “nicotine flux” ECs can overcome some of these limitations, so that nicotine is delivered at a rate that is closer to the rate of delivery from tobacco cigarettes. Indeed, newer generation ECs that deliver nicotine more rapidly are rated as more satisfying compared to older generation ECs that deliver nicotine slowly (3).

Nicotine pharmacokinetics: IV administration protocols to study nicotine reinforcement:

Nicotine administered by IV infusion can be carefully modulated to resemble the nicotine intake from tobacco product use. For example, Rose et al. showed that the pharmacokinetics of nicotine delivered by IV infusion resembles the pharmacokinetics of nicotine delivered via cigarette smoking (8). In this study, the arterial plasma nicotine concentrations from smoking one cigarette was first determined for each subject, then the equivalent dose of nicotine was delivered by IV infusion over a similar time course as smoking a cigarette. Both smoking and IV infusion produced similar arterial (20.5 vs. 20.4 ng/ml) and venous (6.9 vs. 7.8 ng/ml) plasma concentrations of nicotine. The rapid time to peak arterial nicotine concentrations following smoking was also observed for IV infusion (8). Multiple studies have demonstrated that rapid IV nicotine infusion (i.e., less than 60 seconds) elicits positive drug effects (e.g., good effects and

drug liking) similar to smoking, and reinforcing effects (i.e., self-administration) in dependent adult smokers (9-13).

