- 4) PTSD Checklist for DSM-5 (PCL-5):** The PCL-5 is a 20-item self-report measure that assesses the 20 DSM-5 symptoms of PTSD(36). This scale will be used at intake to control for baseline differences in PTSD symptoms

C.2 Study outcome measures

1) Physiological:

- 1.1 Heart rate (HR) and blood pressure (BP) readings will be taken at intake during screening. During the sessions HR and BP will be monitored continuously for medical/safety reasons. The HR and BP responses will help us determine the effect of delivery rate on some of the acute cardiovascular health risks associated with nicotine (36). In our preliminary studies, the peak effect of nicotine versus saline has a large effect size. We will analyze the peak effect

(determined from assessments at min 0, 1, 2, 4, 6, 8, 10, 12, 14, 16, 18 and 20) in our primary analysis because with the peak effect we have the greatest statistical power (>0.8) to detect infusion rate differences. Additional responses will be included in secondary analyses.

2) Biochemical:

2.1 Cotinine levels: Urine cotinine levels will be determined at baseline with a semi-quantitative test strip.

2.2 Alveolar carbon monoxide: CO readings ≤ 10 ppm will be used to verify compliance with overnight smoking abstinence. In our prior work we have used plasma nicotine levels to confirm that smokers with CO ≤ 10 ppm were overnight abstinent with exceptional concordance (95% had plasma nicotine < 10 ng/ml; mean = 2.8 ng/ml (SD 3.1), N=201). The 10 ppm cutoff is higher than cutoffs recommended for distinguishing smokers from non-smokers (~ 5 ppm) but consistent, albeit slightly more conservative, than a suggested cutoff (12 ppm) for distinguishing 8 h abstinent smokers from non-abstinent smokers (25).

3) Drug reinforcement and subjective effects:

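### The 10 h pre-session rule bars smoking but no other nicotine source and is checked only by exhaled CO, although e-cigarette and smokeless users are enrolled

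*Combined protocol and SAP*

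**What the plan says.** Section 9.A (Session procedures) sets the pre-session rule: "subjects will be required to abstain from smoking for 10h, which will be verified by expired air CO levels" at or below 10 ppm. Section 9.C.2, item 2.2, gives the CO reading the same limited purpose: it "will be used to verify compliance with overnight smoking abstinence". Section 11, item 3, again describes the 10 h restriction as one on smoking.

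Other substances are covered separately. Subjects must "refrain from consuming alcoholic beverages and drugs prior study participation, which will be verified by urine drug screening and breathalyzer before the sessions". No nicotine product is named there.

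Section 7 enrols users of non-combusted products on purpose: "We will include users of smokeless tobacco or e-cigarettes given the high prevalence of e-cigarette and smokeless tobacco products among young adults". The only limit is the exclusion for "use of e-cigarettes more than 10 days in the past 30 days"; no limit is stated for smokeless tobacco.

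The evidence for the CO cutoff is in item 2.2: "In our prior work we have used plasma nicotine levels to confirm that smokers with CO" at or below 10 ppm were abstinent overnight. In that work 95% had plasma nicotine below 10 ng/ml, with mean 2.8 ng/ml, SD 3.1 and N=201.

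The baseline row of Fig 2 lists blood and urine samples. It does not name plasma nicotine, as most later rows do.

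**The concern.** Each of the five sessions is meant to start from the same nicotine-deprived state. Here the written rule and its check share a blind spot, and the enrolled population includes people who can fall into it. Exhaled CO marks smoke. That it does not register vaped or oral nicotine is general knowledge rather than something the protocol states, but the protocol itself ties CO only to smoking.

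The starting state matters for the outcomes. Smoking urge is a Specific Aim outcome and is modelled from minute 0. Section 5 (Preliminary Studies) reports lower urges and withdrawal after an IV nicotine session than at the overnight-abstinent baseline. Section 6 argues that slow e-cigarette delivery may be enough to relieve both. Nicotine taken before a session could therefore lower baseline urge and withdrawal and leave less room for the infusion to act. Section 9.A already manages caffeine withdrawal as a possible confounder, and nicotine intake is the more direct one.

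**Working it through.** The protocol states no figure for this point, so the check is mainly of the text. The arithmetic only gives scale.

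**1. Does any listed safeguard cover non-smoked nicotine before a session?**
- Abstinence wording (9.A; 9.C.2 item 2.2; 11 item 3): smoking only.
- CO at or below 10 ppm: tied to smoking only.
- Urine drug screen and breathalyzer (9.A): tied to drugs and alcohol.
- Urine cotinine (Section 7): must exceed 100 ng/mL at entry, so a positive result is expected in everyone. It confirms smoking status and is an optional covariate, not a test of overnight abstinence.
- E-cigarette cap (Section 7): limits frequency before entry and does not govern the session morning.
- Baseline blood (Fig 2): drawn, but no cutoff, rescheduling rule or model term uses a pre-infusion nicotine level.
- CO concordance (item 2.2): reported for smokers in prior work; nothing shows that it was checked in users of other products.

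None of them closes the gap.

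**2. Can permitted use coincide with a session?** Assume use days fall at random, with d use days in 30. The chance that at least one of five sessions falls on a use day is 1 − (1 − d/30)^5.
- d = 1: 1 − (29/30)^5 = 16%
- d = 10 (the cap): 1 − (20/30)^5 = 87%

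These count use at any hour, so under that assumption they overstate use before a session that starts around 8 AM. They show only that the cap does not rule out overlap. They do not estimate how many sessions are affected.

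**3. How large could one exposure be?** Section 5 gives "The peak nicotine concentration in blood, ~8 ng/ml", reached about 12 minutes after the start of 15 puffs.
- Against the abstinent mean: 8/2.8 = 2.9 times.
- If 8 ng/ml is the total level: (8 − 2.8)/3.1 = 1.7 SD above that mean.
- Decay: the protocol gives no half-life. With an assumed 1 to 3 h, 8 × 0.5^(t/half-life) leaves 4.0 to 6.4 ng/ml after 1 h and 2.0 to 5.0 ng/ml after 2 h.

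**4. Would a 10 ng/ml flag on the baseline sample find such sessions?** A subject at the abstinent mean reaches 10 only with a residual of 10 − 2.8 = 7.2 ng/ml, and 7.2/8 = 90% of the full e-cigarette peak. Residuals of 2 ng/ml up to just below 7.2 ng/ml would pass. Conversely, about 5% of CO-passing smokers in the prior work were at or above 10. Over 70 × 5 = 350 sessions that is 350 × 0.05 = 17.5 flags without any vaping, if that rate carries over. A continuous covariate avoids the cutoff.

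**The case against.** The strongest reply is that the exposure may be rare and is partly handled. Everyone smokes 5 to under 20 cigarettes a day, e-cigarette use is capped at entry, and the 10 h before an 8 AM session are mostly overnight. Conditions are randomised to sessions within subject. The DEQ response is a peak change, so the pre-infusion rating is subtracted, and the BQSU model includes minute 0. These points stand and limit the concern. They do not remove it: subtracting baseline corrects an additive shift, not a weaker response to the infusion, and randomisation balances the disturbance on average without removing its variance.

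Three stronger readings are tempting, and the documents do not support them.
- **Pre-session vaping equals an extra study infusion.** Adding the full peak to the abstinent mean gives 2.8 + 8 = 10.8 ng/ml, or 8/3.1 = 2.6 SD above it. The protocol does not say whether the peak is baseline-corrected, and catheter placement and the baseline battery come between arrival and minute 0. The 7.8 ng/ml venous level that invites the comparison comes from a cited study with individually matched doses; the same infusion gave 20.4 ng/ml arterial.
- **Exploratory Aim 2 is corrupted.** That aim uses measured plasma nicotine, which includes nicotine from any source. Fig 2 samples it from minute 1, so the saline session in particular could reveal prior use.
- **The rate contrasts are biased.** With randomised session order the expected effect is noise.

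**Conclusion.** The gap is real and follows from the text alone: a subject who keeps to the stated rule can start a session with recent nicotine on board, and nothing in the plan would detect it or act on it. The consequence is moderate. It adds within-subject noise to the delivery-rate contrasts and makes the baseline urge and withdrawal state less uniform. Menthol preference is not randomised, so that comparison could be biased, but only if e-cigarette or smokeless use differs between the groups, and the documents give no evidence either way. The number of affected sessions cannot be derived from the documents, so no loss of power is claimed. The concentrations above are for scale; the level at minute 0 would be below the peak and depends on time since use. The conclusion assumes that CO does not register non-combusted nicotine. The point should be corrected, but it does not undermine the design.

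**What to change.** - **Rule.** In Section 9.A, extend the 10 h abstinence requirement to all tobacco and nicotine products, naming e-cigarettes and smokeless tobacco. Align the wording in 9.C.2 item 2.2 and Section 11 item 3.
- **Check-in.** Ask about each product at every session and apply the rescheduling rule that 9.A already has for non-compliance. Keep CO as the on-the-day check for smoking.
- **Assay.** State that nicotine will be measured in the baseline blood sample Fig 2 already draws.
- **Analysis.** In Section 10, prespecify a sensitivity analysis that repeats the DEQ and BQSU models with session-level baseline plasma nicotine as a continuous covariate, rather than excluding sessions above a 10 ng/ml cutoff. The sample precedes the infusion, so this does not adjust for an effect of treatment.

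The cost is a wording change, a short check-in question, one assay per session on blood already collected, one extra analysis and probably a few more rescheduled sessions. Sample size and the primary models do not change.
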